**1. Introduction and Purpose:**

Postpartum anemia is a major global maternal health problem. In developing countries, postpartum anemia affects more than two thirds of women. In the United States, it affects 50% of mothers (1) and it has been linked to maternal morbidities such as impaired cognition, depression, and fatigue (2-5). Its negative impact on infant-mother bonding and neonatal care (6) has been reported. A major risk factor for postpartum anemia is iron deficient anemia in the antepartum period. The latter results from physiological changes in pregnancy; total blood volume increases by approximately 50% and red blood cell mass increases by 25% (7). The relative increase of blood volume compared to red blood cell mass causes a physiological anemia of pregnancy and therefore the hemoglobin and hematocrit threshold for diagnosing anemia in pregnancy are different than that of a non-pregnant adult. This increase in red blood cell mass, combined with the needs of the fetus, placenta, and normal anticipated blood loss from vaginal delivery represent a total additional need of 1,000 mg iron for a pregnancy, depleting maternal iron reserve (8-11). Oral iron supplementation is currently the standard of care for women with iron deficiency postpartum anemia (12,13). Up to 40% of patients do not tolerate oral iron (13), mainly due to gastrointestinal effects, leading to poor compliance and persistent anemia (14). Intravenous (IV) iron has advantages that bypass absorption challenges and may lead to faster recovery of iron stores and hemoglobin concentrations (11), with a proven safety record (16-17). Despite its advantages, IV iron is more costly and needs to be administered under supervision in a hospital or outpatient clinical setting. Two major reviews have evaluated the impact of IV iron in the postpartum period (18, 19). The first review did not find differences in maternal fatigue or maternal deaths, but did not report hematological effects such as postpartum hemoglobin. Four new randomized trials have been published comparing IV iron to oral iron therapy (20-23). An updated review of 15 randomized control trials (N=2182) concluded that hemoglobin concentrations at 6 weeks postpartum were almost 1 g/dL higher in women who received IV iron compared to oral iron (19). The safety profile of IV iron was also reassuring. Among the 15 trials included, only 2 were from the United States and neither one had 6 weeks postpartum hemoglobin as primary outcome. Hence, a large multicenter clinical trial is needed to adequately assess the impact of both modalities on hematological effects of postpartum anemia. Our aim is to perform a feasibility trial in order to guide a larger definite trial.

**Brief Study Design and Rationale**

Patients randomly assigned to 2 groups will be compared:

1. **Oral Iron group:** Ferrous sulfate 325 mg (65 mg elemental iron) by mouth for a total of 6 weeks TID.

1.1 IV placebo in sodium chloride 0.9% 500mL infusion will be given before discharge home over 1.5 hour, preceded by placebo test dose IV infusion of 100mL 0.9% sodium chloride.

2. **IV Iron group:** Low molecular weight iron dextran (infed) 1000mg in sodium chloride 0.9% 500mL IV infusion over 1.5 hour, preceded by test dose of 25 mg IV low molecular weight iron dextran infusion in 100mL 0.9% sodium chloride.  
2.1 Oral placebo will be given by mouth for a total of 6 weeks TID.

The standard of care at UTMB for the detection and treatment of postpartum iron deficiency anemia is as follows. All postpartum patients undergo blood draws at their first postpartum day for anemia screening. Those patients who are identified as anemic (hemoglobin < 12 g/dL) then receive oral iron supplementation. There are many different iron supplements that are used at UTMB to treat iron deficiency in pregnancy. These supplements vary in elemental iron content, enteral coatings, and supplements combined with vitamins and minerals. The choice of which iron supplement is left to the discretion of the provider caring for the patient. Among these choices, ferrous sulfate (325mg, with 65mg elemental iron) is very commonly prescribed to UTMB patients and thus is the oral iron therapy that will be used for this study. Standard UTMB treatment surveillance includes blood draws at the 3 and 6 weeks routine postpartum visits. This study will follow the UTMB standard treatment surveillance protocol and thus study participants will have no study specific blood collections.

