#### Study Risks and Benefits:

The known risks of IV iron therapy are minimal infusion reactions: nausea, vomiting, chills, headache, flushing, constipation, mild arthralgia/myalgia of the chest or flank or facial flushing. All of these symptoms routinely abate after therapy, and plasma tryptase levels drawn after the reaction are always normal. The symptoms are most likely due to minor reactions to labile plasma iron released with any of the formulations. Compared to the side-effects present in the majority of people taking oral preparations, such as constipation, metallic taste, gastric cramping and thick green tenacious stool, the adverse events with IV iron are minor, infrequent and short-lasting. Another concern is anaphylaxis, it

has been reported to be very rare (0.6%) with the new IV iron formulation currently in use. IV iron is consequently moving rapidly forward in the treatment paradigm. Published evidence supports a wider and earlier role for IV iron in the management of postpartum anemia and raises the question of whether it should be frontline therapy in such condition.

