## **2. Concise Summary of Project:**

This trial will be a comparative pragmatic double blinded feasibility randomized controlled trial of daily versus IV iron in anemic postpartum patients.

Two randomly assigned groups will be compared during the postpartum period:

1. **Oral Iron group:** Ferrous sulfate 325 mg (65 mg elemental iron) by mouth for a total of 6 weeks TID.

IV placebo in sodium chloride 0.9% 500mL IV infusion will be given before discharge home over 1.5 hour preceded by placebo test dose IV infusion of 100mL 0.9% sodium chloride.

2. **IV Iron group:** Low molecular weight iron dextran (infed) 1000mg in sodium chloride 0.9% 500mL IV infusion over 1.5 hour preceded by test dose 25 mg IV low molecular weight iron dextran infusion in 100mL 0.9% sodium chloride.

2.1 Oral placebo will be given by mouth for a total of 6 weeks TID.

The number of subjects studied will be 40 at UTMB, we plan to approach and consent up to 40 patients to allow for screening failures, early withdrawals, and patients lost to follow-up, and patients who must withdraw due to failure of therapy. This number was decided for the aim as a feasibility trial goal. Study to last an anticipated length of 1 year. If our sample size is not achieved by that time, we will consider the trial as not feasible at UTMB only. This trial will provide important information such as eligibility, consent, and outcomes rates on which to base feasibility and sample size calculations for a larger definitive trial, as well as how many clinical sites would be needed.

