## Screening

All pregnant patients who deliver in our unit undergo a laboratory screen for anemia at the first postpartum day as part of the UTMB standard of care while recovering in the hospital. Eligible patients (PPD#1 patients with a hemoglobin less than 9 g/dl) will be screened and approached while inhouse (detailed under section 8).

The anticipated procedures flow is as follows

1. Research staff will go to postpartum ward.
2. Research staff will confirm with provider that possible subjects are appropriate candidates for treatment with ferrous sulfate.
3. Research staff will approach screened patients to obtain consent from possible subjects.
4. Subjects will be randomized using a computer-generated sequential randomization log with group assignment, subject name, and medical record number.
5. After patient is consented and enrolled, the provider will be notified orders will be placed in EPIC by providers with the assistance of the research staff; and a note will be placed in the electronic chart indicating that the patient is enrolled in the study.
6. Subjects will continue to receive standard, routine postpartum care and surveillance of postpartum iron anemia.
  - a. Research staff and PI will periodically monitor surveillance data by chart review.
7. During their routine 6 weeks postpartum visit, patient's hemoglobin level will be obtained (standard of care at UTMB). If subjects have a hemoglobin level drawn before the 6 weeks visits, such as in the 3 weeks postpartum visit, we will also collect this information.
8. Research staff will conduct chart review to obtain the data points for the primary and secondary outcomes (described in section 1)

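### Minor: the intention-to-treat set starts at tablet dispensing rather than at randomization, so a randomized woman can be left out of the primary analysis

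*Combined protocol and SAP*

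**What the plan says.** Section 2 describes a "comparative pragmatic double blinded feasibility randomized controlled trial". Under Brief Study Design and Rationale, the oral arm takes ferrous sulfate three times daily and receives a placebo infusion. The intravenous arm receives a 25 mg test dose and then 1000 mg of iron dextran, and for its tablets "Oral placebo will be given by mouth for a total of 6 weeks TID".

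Section 4 gives the sequence as consent and randomization, an order in the electronic record, dispensing by the Investigational Drug Service (IDS) according to assignment, delivery to the ward, and administration by the nurse. A later paragraph of section 4 says that a woman enters the intention-to-treat analysis when IDS has dispensed her tablets and the sequence number is on her randomization form. Section 13 states that the primary analysis is by intention to treat and adds no restriction. Section 3, Additional details, keeps women who need transfusion in that analysis. It says nothing about women to whom no tablets were dispensed. Section 7 takes the outcomes from chart review.

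**The concern.** Intention to treat protects the comparison because membership is fixed at randomization, before anything that treatment can influence. Here membership waits for a later event. The documents do not say whether the tablet bottle reaches the woman before the infusion, with it, or afterwards at discharge. If afterwards, a reaction to the test dose or a stopped infusion could lead to withdrawal before the tablets are dispensed, and that woman would drop out of the analysis. Only the intravenous arm receives active iron dextran, so such omissions could fall unevenly and would remove women in whom that strategy failed. Section 2 itself expects "patients who must withdraw due to failure of therapy".

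There is a related, smaller gap: the available text has no step for an infusion that is missed or stopped, although the tablets may be placebo.

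**Working it through.** **The plan's own figure.** Section 13 uses d = 0.9592329, two-sided alpha 0.05 and 19 per group.
- Noncentrality: 0.9592329 × √(19 × 19 / 38) = 2.9566. With critical t = 2.0281 on 36 df, power is 0.8204, as printed.
- 38 / 0.95 = 40 randomized. At 1:1 allocation that is 20 per arm.

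**Order of events, from section 4.** Dispensing follows randomization; that much is stated. The infusion is before discharge (stated for the placebo infusion, and implied for the iron infusion by blinding). The time of tablet dispensing is not stated. Two cases follow.
- *Tablets dispensed before the infusion.* A woman omitted at this stage has had no treatment. If those deciding are blind, the omission should not depend on arm. Numbers are lost and little bias arises.
- *Tablets dispensed after the infusion.* Omission can depend on what happened during an infusion that differs between arms. The exclusion can then be selective.

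The documents do not allow a choice between these cases.

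**Size per woman.** 1 / 20 = 5% of an arm.

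**Effect on power.** Assume m of the 40 are dropped before dispensing and 5% of the rest are then lost:

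| m | Evaluable | Power |
|---|---|---|
| 0 | 38 | 0.820 |
| 1 | 37 | 0.809 |
| 2 | 36 | 0.798 |
| 3 | 35 | 0.786 |
| 4 | 34 | 0.774 |

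Power falls by about one percentage point per woman. It is not the reason for change.

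**Effect of one selective omission (illustration).** Assume one of 20 intravenous-arm women gets essentially no iron and her expected 6-week hemoglobin is 11.2 − x g/dL, with x from 0 to 1.0. The planned difference is 12.4 − 11.2 = 1.2. Keeping her gives 1.2 − (1.2 + x)/20.
- x = 0: 1.2 − 0.06 = 1.14 g/dL
- x = 1.0: 1.2 − 0.11 = 1.09 g/dL

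Leaving her out restores 1.2, so the estimate is too favorable by 0.06 to 0.11 g/dL. The count and x are assumptions; no failure rate for infusions is given.

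**Secondary gap.** A woman stopped after the test dose has had 25 / (25 + 1000) = 2.4% of her planned iron. Under usual care, "Those patients who are identified as anemic (hemoglobin < 12 g/dL) then receive oral iron supplementation". The next scheduled hemoglobin is at about 3 × 7 = 21 days: "Standard UTMB treatment surveillance includes blood draws at the 3 and 6 weeks routine postpartum visits". It is at 6 × 7 = 42 days if the 3-week draw is not done, which Screening step 7 allows for.

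**The case against.** **On the analysis set.** Section 4 can be read as IDS sending everything to the ward before any treatment. Omissions would then precede treatment and, under blinding, be balanced. The sentence might also be meant only to fix inclusion whatever happens later, and section 13 claims intention to treat without qualification. Both readings are possible. Neither settles the matter, because the tablet-bottle step is not timed and the sentence as written makes dispensing the condition for entry. It does stand that no omission is documented as likely.

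**On the missed infusion.** A reader might infer that the protocol leaves a severely anemic woman untreated on placebo. The documents do not support that.
- The infusion takes place in hospital, its administration is charted, and unused drug goes back to IDS (section 4).
- Providers are educated about the trial (section 8) and notified of enrollment (Screening, step 5).
- "Subjects will continue to receive standard, routine postpartum care and surveillance of postpartum iron anemia", and nothing in the available text bars open-label iron.
- Additional details says that surveillance will pick up treatment failure and that it will be dealt with.
- The information for a code-break exists in the "computer-generated sequential randomization log with group assignment, subject name, and medical record number" and at IDS.

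What is absent is a written step tied to the failed infusion and a code-break procedure.

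**On frequency.** A reader might size this risk from anaphylaxis, which "has been reported to be very rare (0.6%) with the new IV iron formulation currently in use": 20 × 0.006 = 0.12 expected cases, and 1 − 0.994^20 = 11.3% for at least one. That figure should not be used. Anaphylaxis is the cause least likely to go unnoticed. Lost access, refusal, early discharge and mild reactions matter more here, and the documents give no rate for them.

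**Conclusion.** The analysis-set point holds and is minor. Section 4 states an entry rule that follows randomization and does not match the intention-to-treat analysis named in section 13. Each woman left out is 5% of her arm, and the frequency is unknown. The effect on power is small. Selective exclusion is possible only if tablets can follow the infusion, which the documents neither state nor rule out. The shift of 0.06 to 0.11 g/dL per woman is an illustration that rests on assumed values.

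The missed-infusion gap is a request for clarification only. It does not show that women would go untreated, and it does not raise the severity. Consent pages were not available, so any wording there on stopping or alternative treatment could not be checked.

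**What to change.** **Main change.** Replace the entry sentence in section 4 with: *All randomized women are analyzed in their assigned arm, whether or not the infusion was completed or tablets were dispensed.* Take outcomes from chart review where available. This is one sentence by amendment, with no added visits or blood draws. The downside is slight dilution from untreated women, which an intention-to-treat estimate is meant to include.

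**Secondary clarification.** Add to section 4, for both arms: if the test dose or infusion is not given or not completed, the treating provider is told the same day that the study tablets may be placebo, and may replace them with open-label iron. Replace, not add, because oral-arm tablets already supply 65 × 3 = 195 mg of elemental iron a day. Applying the rule to both arms means that it does not itself reveal the assignment. Its costs are some blurring of the contrast between arms, lost tablet-compliance data for the women affected, and possible unblinding, which could influence their self-reported fatigue and depression scores.

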#### Primary outcomes:

- Postpartum hemoglobin and hematocrit at 6 weeks postpartum visit

#### Secondary outcomes:

- Assessment of adverse effects (such as: arthralgia, backache, chills, dizziness, moderate to high fever, headache, malaise, myalgia, nausea, and vomiting)
- Analysis of CBC indices including reticulocyte count, MCV, etc.
- Iron studies at time of diagnosis (Total Iron binding capacity, Ferritin, serum Iron levels: this panel measures the amount of iron used from the body's stored iron in contrast to reticulocyte counts that measures amount of red blood cells the bone marrow is making).
- Need for transfusion in the peripartum period
- Postpartum hemoglobin and hematocrit
- Neonatal weight
- Postpartum fatigue (multidimensional fatigue inventory (MFI) instrument validated by Smets et al.) at 6 weeks visit.
- Postpartum depression (Edinburgh postnatal depression scale) at 6 weeks visit.
- Neonatal outcomes such as NICU admission, hyperbilirubinemia, and APGAR scores
- Relationship of obesity to effectiveness of supplementation in both study arms
- Drug compliance

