## **4. Disposal and Administration of Drug and Placebo/Drug compliance**

The intervention drugs (IV/PO Iron and placebo) will be provided by Greenpark Compounding Pharmacy and UTMB Investigational Drug Service (IDS). The latter will receive, store and dispense the drugs for the study.

Once a qualified subject is consented and randomized, an order will be entered in Epic. The UTMB IDS will be notified to dispense the study drug according to the treatment assignment per study protocol. The assigned drug and placebo will be delivered to the nursing unit to be administered by the nurse assigned to the subject. The assigned nurse will document the administration in Epic using Medication Administration Record (MAR). Any unused study drug will be returned to IDS for documentation and disposal. Medications used in this study will not be billed to the subject or her insurance company.

The IDS will dispense the pills in a container/bottle and the subject will be given the bottle and given instructions to come to clinic at 6 weeks postpartum to see provider with bottle/container. The supplies given will be enough for total treatment of 6 weeks.

The subject will be included in the analysis by intent-to-treat once the assigned pills are dispensed from IDS and sequential number posted on the subject specific randomization form.

Drug compliance: subject will be instructed to bring pill container to all clinic visits. The provider will document number of pills in the container in order to account for compliance at best in each postpartum visit and emphasize compliance. At the end of the treatment period (6 weeks postpartum visit), the research team will collect the container and count the returned pills prior to returning it to the IDS for reconciliation within 2 weeks of receiving the bottle. Study participation will end at 6 weeks postpartum. However, if subject does not come to their scheduled postpartum visits, we will do our best to attempt to contact and retrieve drug container up to 10 weeks postpartum.

If subject misses her regular postpartum visit, we will make every effort to contact the subject by phone and enquire about the outcomes.

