## **7. Sources of Research Material:**

The primary and secondary outcomes for this trial will be obtained from chart review for enrolled patients.

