## **12. Potential Benefits:**

The potential benefits of the study to the intervention group (IV iron) include:

1. Improved fractional absorption of iron with corresponding improvement of anemia compared to standard oral iron replacement therapy
2. Decreased GI side effects with IV iron
3. Faster increase in hemoglobin

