## **13. Biostatistics:**

We hypothesize that the IV iron group will have a higher hemoglobin level at 6 weeks postpartum compared with the oral group. The primary analysis will be conducted on an intention-to-treat basis. Between-group differences in continuous variables will be assessed using Student t test or Man-Whitney rank sum test and results will be given as mean, standard deviation or median range as appropriate. Categorical variables will be assessed using the Pearson chi-square test or Fisher exact test as appropriate. For dichotomous endpoints, relative risk (RR) and 95% CI values will be calculated. P <0.05 will be considered significant. The analysis will be performed after study completion.

Based on data from the literature, we estimate that women who received oral iron will have a mean 6 week postpartum hemoglobin of 11.2 g/dL with a standard deviation of 1.2. We anticipated that women that receive IV Iron will have a postpartum 6 weeks mean hemoglobin of 12.4 g/dL. Using calculated effect size, power of 80% and 2-sided alpha of 0.05, we estimate that we will need 38 (19/group) subjects with complete ascertainment. Accounting for 5% lost to follow up, the final sample size would be **40**.

We will be performing a superiority approach. Stata 16 will be used for the statistical analysis.

**t tests - Means:** Difference between two independent means (two groups)

**Analysis:** A priori: Compute required sample size

**Input:** Tail(s) = Two

Effect size d = 0.9592329

$\alpha$  err prob = 0.05

Power (1- $\beta$  err prob) = 0.8

Allocation ratio N2/N1 = 1

**Output:** Noncentrality parameter  $\delta$  = 2.9565544

Critical t	=	2.0280940
Df	=	36
Sample size group 1	=	19
Sample size group 2	=	19
Total sample size	=	38
Actual power	=	0.8203999

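### The named adverse effects include none of those the protocol attributes to oral iron, and chart review without a symptom checklist risks under-recording them.

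*Combined protocol and SAP*

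**What the plan says.** All references are to the combined protocol and SAP.

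- **Outcome.** Section 1, Secondary outcomes, opens with "Assessment of adverse effects (such as: arthralgia, backache, chills, dizziness, moderate to high fever, headache, malaise, myalgia, nausea, and vomiting". The words introducing the list make the terms examples.
- **Effects named for oral iron.** Study Risks and Benefits refers to "side-effects present in the majority of people taking oral preparations, such as constipation, metallic taste, gastric cramping and thick green tenacious stool".
- **Effects named for IV iron.** The same section gives "minimal infusion reactions: nausea, vomiting, chills, headache, flushing, constipation, mild arthralgia/myalgia of the chest or flank or facial flushing". It also mentions anaphylaxis, at 0.6%.
- **Role of gastrointestinal (GI) tolerability.** The introduction says "Up to 40% of patients do not tolerate oral iron (13), mainly due to gastrointestinal effects, leading to poor compliance and persistent anemia". Section 12 lists "Decreased GI side effects with IV iron" as a potential benefit.
- **Data source.** Section 7 states "The primary and secondary outcomes for this trial will be obtained from chart review for enrolled patients", and section 3 (Outcomes) says the same of the secondary outcomes. For a missed visit, section 4 adds that "we will make every effort to contact the subject by phone and enquire about the outcomes".
- **Analysis.** Section 13 plans chi-square or Fisher tests for categorical variables and adds "For dichotomous endpoints, relative risk (RR) and 95% CI values will be calculated". It gives no GI endpoint or hypothesis.
- **Use of the results.** Section 2 describes a 40-patient, double-blind feasibility trial that is to supply outcome rates for a larger one.

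**The concern.** GI intolerance of oral iron is part of the protocol's case for the IV route: it is the stated main cause of intolerance and poor compliance, and its reduction is an offered benefit. The symptoms that would show it are not among the named effects, and nothing prompts staff to ask about them.

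The setting adds to this. The infusion is given by a nurse on the ward. The pills are taken at home for six weeks, and a complaint reaches the data only if the patient raises it and a clinician writes it down.

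Three things are at stake. The potential benefit in section 12 has no measure matched to it. The tolerability picture may tilt against IV iron. The GI rates handed to the definitive trial may be too low, and compliance, itself a secondary outcome, would be hard to interpret without them.

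**Working it through.** **Step 1. Compare the lists** (Secondary outcomes against Study Risks and Benefits).

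| Named in the outcome | Named for IV iron | Named for oral iron |
|---|---|---|
| Nausea, vomiting, chills, headache, arthralgia, myalgia | Yes | No |
| Backache, dizziness, fever, malaise | No | No |

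Six of the ten terms match IV iron, four match neither route, and none matches oral iron. Of the four oral-iron effects, 0 of 4 are listed. One of them, constipation, is also named for IV iron, so its absence concerns both arms.

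**Step 2. Check how effects are collected.** Chart review is the source for every secondary outcome. No checklist, recall window or collection schedule is given for any adverse effect, listed or not. The only direct enquiry described that could reach these symptoms is the phone call after a missed visit, and it is not said to cover them.

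**Step 3. The plan's own figure.** The documents give no sample size or power for adverse effects. The haemoglobin calculation reproduces: with d = 0.9592329 and 19 per group, noncentrality = 0.9592329 × √(19/2) = 2.9566, critical t (36 df) = 2.0281 and power = 0.820. Allowing for 5% loss, 38/0.95 = 40. This has no bearing on adverse effects beyond fixing 20 per arm.

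**Step 4. Illustrate the size.** Let p₁ and p₂ be the true proportions with any oral-type GI effect in the oral and IV arms, and s the fraction of events that reach the chart, taken as equal in both arms. The recorded proportions are s·p₁ and s·p₂. Power is the sum, over all pairs of counts (a, b) with two-sided Fisher p < 0.05, of Bin(a; 20, s·p₁) × Bin(b; 20, s·p₂).

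For p₁, 60% is one reading of the protocol's word for most users, and 40% borrows the upper figure for intolerance in the introduction. The values of p₂ and s are assumptions; the documents give neither.

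| True rates, oral v IV | Power, all recorded | Recorded rates, s = 0.5 | Power, s = 0.5 |
|---|---|---|---|
| 60% v 15% | 0.80 | 30% v 7.5% | 0.33 |
| 40% v 10% | 0.49 | 20% v 5% | 0.17 |
| 60% v 30% | 0.35 | 30% v 15% | 0.12 |
| 40% v 20% | 0.19 | 20% v 10% | 0.07 |

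**Step 5. What equal under-recording does to the estimates.** The relative risk is unchanged: 60/15 = 4 and 30/7.5 = 4. The rates and the risk difference are halved: 60 − 15 = 45 points becomes 30 − 7.5 = 22.5 points. For a given symptom the damage is therefore to the rates and to precision, not to the direction of the comparison.

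**The case against.** - **The list is open.** Nothing excludes constipation, cramping or taste change from the outcome. This stands: a reader might infer that the GI advantage cannot be tested, and the text does not support that. But an open list helps only if someone asks, and no one is assigned to.
- **No listed effect is solicited either.** This stands. A reader might infer that IV-type reactions are actively sought while oral-type effects are not, but the documents describe the same chart review for all. The asymmetry comes from where the symptoms arise, not from a stated difference in method.
- **Blinding.** Each arm receives a placebo of the other route, so a given symptom is recorded under like conditions in both arms. A reader might infer that the comparison is biased against IV iron. That is not shown, and any overall tilt would depend on how effects are summarised, which the plan does not say. Blinding does not, however, recover symptoms that were never charted.
- **The list is not purely infusion-type.** Nausea and vomiting are GI effects and will be compared. Four terms are tied to neither route. Both points stand.
- **There is no GI hypothesis.** Correct: fewer GI effects is a potential benefit, and the stated hypothesis concerns haemoglobin. The case for change rests on rates, not on a failed test.
- **Power is weak anyway.** Also correct. Under several assumed rates, full recording leaves power below one half.
- **Anaphylaxis is not listed.** It need not be a compared outcome. Section 10 already provides for quarterly summaries of adverse and serious adverse events and reporting under IRB policy. At 0.6%, the chance of at least one event in 20 IV patients is 1 − 0.994²⁰ = 0.11.

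**Conclusion.** The point holds as a risk of under-ascertainment. None of the four effects the protocol names for oral iron is in the outcome list, against six terms it names for IV iron, and no prompted collection is described for any effect. That infusion reactions on the ward will be charted more fully than GI complaints at home is a reasonable expectation, not a documented fact.

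If charts catch half of the events, recorded GI rates are halved. Power at the more favourable assumed rates then falls from 0.80 to 0.33 (60% v 15%) and from 0.49 to 0.17 (40% v 10%). These figures rest on assumed IV-arm rates and an assumed, equal capture fraction. Full recording gives anything from 0.19 to 0.80 across the pairs shown, so 0.80 should not be read as what a checklist would deliver. The consequence that matters most is the effect on rates carried forward to the definitive trial. The change is cheap and worth making before enrolment.

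**What to change.** 1. Name constipation, metallic taste, gastric cramping and stool change in the adverse-effect outcome in section 1.
2. Ask one fixed checklist of all listed effects, in the same words and with a stated recall window, in both arms at the routine 3- and 6-week visits. After a missed visit, use the same checklist in the phone call already planned.
3. Amend section 7 so that the checklist, alongside chart review, is a source for this outcome.
4. In section 13, report the proportion with each effect by arm with a confidence interval, and present the GI comparison as descriptive.

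The cost is a one-page form, a few sentences of protocol text and a few minutes of staff time per visit. No visit is added, and fatigue and depression instruments are already planned at six weeks.
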